7.2.1 Reporting of Immediately Reportable Events

The following events, regardless of severity or seriousness, are considered immediately reportable IREs and are to be reported via the IRE Form within 24 hours to the Sponsor or designee:

- All Serious Adverse events;
- All pregnancies; and
- Events of Special Interest (list all events of special interest).
 - Chest pain/chest discomfort
 - Dyspnea/shortness of breath/difficulty breathing
 - Hepatotoxicity/liver enzyme increased
 - Anaphylaxis, including anaphylactoid reaction and anaphylactic shock

Immediately Reportable Events, such as SAEs, should be recorded on the Adverse Event source document and eCRF. In addition, any IRE occurring during the clinical study must be reported within 24 hours to the Sponsor or designee using the IRE form. The initial report of an IRE must be documented on the study IRE form, signed by the Investigator and submitted by facsimile. The Investigator must provide the following information: protocol number,

subject's initials and study number AE term and associated dates, causal relationship between the event and study medication, relevant history, study medication dosing details, full description of the event, and other required data within the IRE form. All oral reports of an IRE must be followed immediately by a facsimile of the IRE form signed by the Investigator. Investigators should not leave oral reports of IREs on any voicemail aside from the Sponsor's Medical Monitor or designee. The details of the adverse event reporting requirement are also outlined in a safety reporting plan.

The Sponsor assumes responsibility for reporting of expedited and periodic safety reports to the appropriate regulatory authorities. The Sponsor will report to the Investigator any new safety events occurring in other studies. The Investigator may need to report SAEs to the appropriate IRB/IEC in accordance with local regulations.

7.2.1.1 Reporting of Pregnancies

Any pregnancy occurring in a female subject after the first intake of study medication, while not an AE, is considered an IRE. It must be reported within 24 hours of the Investigator learning of the event using an IRE Pregnancy Report Form. Any subject, who becomes pregnant, shall be removed from the clinical study and followed for the duration of the pregnancy. Follow-up information regarding the outcome of the pregnancy and any postnatal sequelae in the infant up to one year of age will be required.

7.2.2 Outcome

The investigator should follow all IREs until resolution (return to baseline status) or loss to follow-up or until no further improvement or worsening of the participant's condition is expected. Loss to follow-up implies that the Investigator site is no longer aware of the participant's whereabouts, and is unable to obtain current contact information. All attempts to contact the participant must be captured in the appropriate trial source document.

7.2.3 Symptoms of the disease under study

Symptoms of the disease under study should not be classed as AEs as long as they are within the normal day-to-day fluctuation or expected progression of the disease. However, significant worsening of the symptoms should be recorded as an AE.

7.2.4 Clinical laboratory evaluations

A change in the value of a safety laboratory investigation can represent an AE if the change is clinically relevant or if, during treatment with the investigational product, a shift of a parameter is observed from a normal value to a pathological value, or a further worsening of an already pathological value. When evaluating such changes, the extent of deviation from the reference range, the duration until return to the reference range, either while continuing treatment or after the end of treatment with the investigational product, and the range of variation of the respective parameter within its reference range, must be taken into consideration.

If, at the end of the treatment phase, there are pathological laboratory values which were not present at baseline, per investigator discretion further clinical or laboratory investigations should be performed until the values return to within reference range or until a plausible explanation (e.g., concomitant disease) is found for the pathological laboratory values.

The Investigator should decide, based on the above criteria and the clinical condition of a subject, whether a change in a laboratory parameter is clinically significant and therefore represents an AE.

7.2.5 Vital Signs

A change in the value of a vital sign measurement can represent an AE, as discussed in Section 6.3 for blood pressure and heart rate. The Investigator should decide, based on the criteria in Section 6.3, or per their discretion (for other vital sign measurements), and the clinical condition of a subject, whether a change in vital signs is clinically significant and therefore represents an AE.

7.2.6 Overdose

There are no specific treatments or monitoring guidelines prescribed for subjects with lubiprostone overdose. It will be left to the discretion of the Investigator's clinical judgment on how to provide appropriate symptomatic treatment.

Any incidences of overdose with the investigational product will follow the same reporting procedures as an AE (see Section 7.2), and only where applicable, as an IRE (see Section 7.2.1).

7.3 Contacting Sponsor Regarding Safety

Any medical safety related issue regarding the conduct of the trial needs to be addressed by the Medical Monitor. The names of the individuals (and corresponding telephone numbers) who should be contacted regarding safety issues are listed on the Sponsor Contact Information page in the front section of this protocol.

7.4 Coding of Adverse Events

All AEs will be coded by the Sponsor's designee using the current Medical Dictionary for Regulatory Activities (MedDRA)® terminology.

7.5 Monitoring of Safety Data

A Data Safety Monitoring Board (DSMB) will monitor safety data on a regular basis throughout the study. Specific details, including meeting frequency and stoppage criteria, are provided in the DSMB Charter.

8. STATISTICAL METHODS AND DATA MANAGEMENT

The statistical analyses described in this section will be performed for the core study as further outlined in the SAP, which will be finalised prior to database lock and will be included in the Clinical Study Report for this protocol. Due to the titration aspect of the preceding double-blinded study (SAG/0211PFC-1131), bottles will not specifically identify whether they contain lubiprostone 12 or 24 mcg so as to maintain the prior blind. Dose assignment will only be known in subjects who were at least 50 kg in weight at the time of randomisation in the preceding study (SAG/0211PFC-1131). All dose assignments will be handled by the IXRS and will continue to maintain blinding with respect to the treatment assignment in the preceding trial. Investigators will be provided with subject treatment dose information associated with their study participants upon finalisation of the Clinical Study Report.

8.1 Determination of Sample Size

The sample size goal is based on the expected attrition that would occur and the remaining number of safety evaluable subjects at each timeframe during the study.

8.2 Datasets Analysed

Two analysis populations, Safety population and the modified Intent-to-Treat (mITT) population and these will be defined as follows:

- **The Safety population** will consist of all enrolled subjects who take at least one dose of study medication.
- **The mITT population** will include all enrolled subjects who take at least one dose of study medication and have at least one treatment period diary entry.

8.3 Analysis of Subject Characteristics and Completion Status

Subject demographic data will be summarized by treatment group and overall with descriptive statistics. The summaries will include mean, median, standard deviation, minimum and maximum for continuous variables, and counts and percentages for each level of categorical variables.

Baseline disease status will be assessed by constipation history, baseline period assessments of the subject's evaluation of BM frequency rates, SBM frequency rates, stool consistency, bowel straining, abdominal pain, constipation severity, incontinence episodes, occurrence of large diameter stools, retentive posturing, and the health-related quality of life using the PedsQL™ questionnaires. These data will be summarized with descriptive statistics as outlined above.

8.4 Analysis of Exposure to Study Medication, Rescue Medication, and Concomitant Medication

Assessments of actual exposure to study medication and rescue medication will be made based on the eCRF and diary data. Results will be summarized by descriptive statistics.

Concomitant medications will be classified by the World Health Organization (WHO) medical dictionary, and numbers and percentages of subjects receiving each classified medication will be calculated for all medications.

8.5 Analysis of Safety

8.5.1 Deaths, Serious Adverse Events, and Adverse Terminations

Subjects with these critical events will be identified in separate listings, with the event, timing and outcome information and relevant demographic and baseline data.

8.5.2 Adverse Events

The original terms used in the eCRF by Investigators to identify AEs will be coded to MedDRA® system organ class and preferred terms. Adverse events will be summarized in terms of incidence per dose group and overall. The incidence of an AE is defined as the number of subjects who experienced at least one episode during the study. Adverse event incidence rates will be summarized by system organ class (SOC) and preferred term (as determined by the coding).

Whatever the level of classification, if a subject experiences multiple episodes of an event within the given time reference, then the event is only counted once. Further, for summaries by severity or causality, the most severe event is chosen for a subject if that subject experiences multiple episodes of the same event.

In this study, faecal impaction and bone fractures will be captured as AEs. The events of faecal impaction will be used for the analysis of the faecal impaction frequency during the study (see [Section 8.6.2.6](#)).

AEs with onset dates after administration of the first dose of study medication or prior to the last day of treatment + 7 days will be considered treatment-emergent. Events with completely or partially missing onset dates will be included in the tabulations, unless the available partial date information clearly indicates that the event happened outside of the treatment period.

P-values from Fisher's exact test or chi-square test will be presented in the AE summary tables. The test will be performed to compare incidence rates at the SOC and "At Least One Event" level between the two treatment groups.

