SNRI	Serotonin –Norepinephrine Reuptake Inhibitor
SOC	System Organ Class
SSRI	Serotonin-Specific Reuptake Inhibitor
WBC	White Blood Cell
WHO	World Health Organization

PROTOCOL SYNOPSIS

A Multicentre, Long-term Safety, Efficacy and Pharmacokinetics Study of Lubiprostone in Paediatric Subjects Aged ≥6 to <18 years with Functional Constipation		
Study Phase	Phase 3	
Short Title	Long-term safety extension study of lubiprostone for the treatment of paediatric functional constipation in subjects aged ≥6 to <18 years	
Objectives, Study Medication and Dose Regimen:	
To assess the long-term safety, efficacy, and pharmacokinetics of oral lubiprostone 12 or 24 mcg capsules dosed twice daily (BID) when administered orally for 36 weeks in paediatric subjects with functional constipation. Evaluation of lubiprostone safety is the primary objective in this study.
 
Dose assignment will be based on the dose they were receiving at the time of rolling over from the preceding, double-blind study (SAG/0211PFC-1131) into this safety extension study for those subjects who were randomised to receive lubiprostone during the preceding study. For subjects who received placebo during the preceding study, assignment of dose will be assigned based on subject body weight at the time of rollover to this extension study. All dose assignment will be handled by an Interactive Voice/Web Response system (IXRS) and will continue to maintain blinding with respect to the treatment assignment in the preceding trial.
	
Assumed No. of Sites:	Approximately 130 (Northern America and Europe)	
Est. No. Enrolled Subjects:	415 subjects who completed Study SAG/0211PFC-1131	
Est. No. Screened Subjects:	NA	
Duration of Participation:	Up to 42 weeks (including follow-up)	
Duration of Treatment:	36 weeks	
Study Schedule:	Visit 9: Enrolment (Clinic Visit)	Day 1 (coincides with SAG/0211PFC-1131 study Visit 7)
	Visit 10: Interim Treatment Visit (Clinic Visit)	Week 1 Visit (±2 days)
	Visit 11: Telephone Assessment	Week 4 Visit (±3 days); Month 1
	Visit 12: Interim Treatment Visit (Clinic Visit)	Week 12 Visit (±3 days); Month 3
	Visit 13: Telephone Assessment	Week 16 Visit (±3 days); Month 4
	Visit 14: Interim Treatment Visit (Clinic Visit)	Week 24 Visit (±3 days); Month 6
	Visit 15: Telephone Assessment	Week 28 Visit (±3 days); Month 7
	Visit 16: End-of-Treatment (Clinic Visit)	Week 36 Visit (+3 days); Month 9
	Visit 17: Follow-Up (Clinic Visit)	Week 40 Visit (+3 days); Month 10

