Sample Size Estimate Calculation	
For purposes of establishing the safety profile with lubiprostone long-term exposure in paediatric functional constipation, safety data from subjects enrolled in this study will be considered together with the 100 subjects enrolled in Sucampo study SAG/0211PFC-11S2 (subjects in this study will be below 6 years old).
 
The sample size is based on the expected attrition that would occur and the remaining number of safety evaluable subjects at each timeframe during the study.

Statistical Methodology	
Efficacy analysis will be based on modified intent-to-treat (mITT) population which includes all enrolled subjects who take at least one dose of study medication and have at least one treatment period diary entry. Categorical and discrete variables will be summarized by counts and percentage, and continuous variables will be summarized by descriptive statistics. Detailed statistical methodology will be documented in the Statistical Analysis Plan (SAP).
 
Adverse events will be summarized in terms of incidence by treatment group and overall. Changes from baseline or clinical abnormalities in clinical laboratory data, physical examinations, and vital signs will be summarized by treatment group and overall.
 
The PK profile for lubiprostone will be determined from the concentration-time data for all evaluable subjects based on the plasma concentrations lubiprostone (if measurable) and of lubiprostone's metabolite, M3. Actual post-dose sampling times relative to time of study medication administration, rather than scheduled sampling times, will be used in all PK profile computations involving sampling times.

SCHEDULE OF EVALUATIONS

Study Week(s) / Month(s)	0	1 / 0	4 / 1	12 / 3	16 / 4	24 / 6	28 / 7	36 / 9	40 / 10
Study Day(s)	1	8 (± 2)	29 (± 3)	85 (± 3)	113 (± 3)	169 (± 3)	197 (± 3)	253 (+ 3)	281 (+ 3)
Visit Number	9	10	11	12	13	14	15	16	17
Visit Type	Enrolment ¹	Clinic Examination	Telephone Assessment	Clinic Examination	Telephone Assessment	Clinic Examination	Telephone Assessment	End-of-Treatment Clinic Examination	Follow-up Clinic Examination
Assessment									
Informed Consent/Assent	X								
Inclusion/Exclusion Criteria Review	X								
Demographics	(V1)								
Medical History	(V1/V2)								
Vital Signs, Height, and Weight ²	(V7)	X		X		X		X	X
Physical Examination ³	(V7)	X		X		X		X	X
Pharmacokinetic Sampling ⁴	X								
Blood Chemistry, Hematology, Urinalysis	(V7)	X		X		X		X	X

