Pregnancy Test ⁵	(V7)	X		X		X		X	X
Concomitant Medications									
Adverse Events									
BMD and BMC Assessments ⁶	(V7)							X	
Study Medication Distribution ⁷	X	X		X		X			
QoL Assessment	(V7)			X		X		X	
Study Treatment									
Study Medication Collection		X		X		X		X	
Electronic Diary ⁸									

Note: The Visit numbers in parentheses are in reference to the preceding placebo-controlled study (SAG/0211PFC-1131).

¹ The End-of-Treatment Visit (V7) in study SAG/0211PFC-1131 will serve as the Enrolment Visit and the corresponding assessments are designated above as "V7". Other corresponding visits from preceding study are also designated by the visit number;

² Measure predose vital signs at Visit 9, as well as measurement of heart rate and blood pressure 1 hour after the first dose of study medication. If blood pressure and/or heart rate are, according to the Investigator, clinically significantly elevated relative to predose at the 1 hour postdose measurement, additional measurements should be taken again at 2 hours and 3 hours postdose. Subjects should be asked to remain seated for at least 5 minutes prior to measurement of vital sign parameters. A wall-mounted stadiometer, where available, should be used for measurement of height. Vital sign assessments will be performed prior to PK sampling when these assessments are collected at the same visit. Record the time of all vital sign measurements in the source documents. Age-appropriate equipment, e.g., blood pressure cuffs, should be used for all assessments;

³ Complete comprehensive physical examinations at Enrolment and End-of-Treatment visits. An abbreviated physical examination is to be performed at all other visits;

⁴ PK samples will be collected predose and 1 sample between 30 and 90 minutes after dose administration (2 samples total). PK samples will be taken under non-fasting conditions. The samples will be collected via direct venipuncture. Approximately 8 mL of blood will be taken for each sample such that the total of all PK samples does not exceed 50 mL or 5 mL/kg of body weight;

⁵ Urine pregnancy tests will be performed at all study visits on subjects of childbearing potential.

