4.2 Exclusion Criteria

Subjects who meet any of the following criteria will be excluded from participating in the study:

1. Subject has current evidence of untreated faecal impaction.
2. Subject has experienced an adverse event during the SAG/0211PFC-1131 study which the Investigator considers to be clinically significant and would limit the subject's ability to participate in the trial.
3. Subject has had a significant change in their medical status, newly diagnosed and uncontrolled cardiovascular, liver or lung disease, neurologic or psychiatric disorder, or other systemic disease, which the Investigator considers to be clinically significant and would limit the subject's ability to participate in the trial.

4. Subject has developed an abnormal laboratory test (haematology, urinalysis, or blood chemistry), which in the Investigator's opinion is clinically significant and would limit the subject's ability to participate in the trial.
5. Subject (female of childbearing potential) has a positive pregnancy test, refuses/is unwilling to undergo pregnancy testing, and/or does not agree to use protocol-specified contraceptive measures for the duration of the study.
6. Subject demonstrated non-compliance with study protocol (i.e., dosing schedule, visit schedule, diary completion, or study procedures) during the SAG/0211PFC-1131 study.

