Normal blood pressure ranges will be based on the National Institutes of Health National Heart, Lung, and Blood Institute chart ([Appendix 2](#)). If, at 1 hour postdose, a change in blood pressure of greater than 15 mmHg from the predose assessment is observed, and this change is confirmed by a repeat measure, additional measurements must be taken at 2 and 3 hours postdose. If the observed change is sustained through the three post-dose measurements, it should be considered a clinically significant change, which must be reported as an adverse event.

Normal heart rate ranges will be based on the Silverman pediatric ranges ([Appendix 3](#)). If, at 1 hour postdose, a change in heart rate of greater than 20 beats per minute (bpm) from the predose assessment is observed, and this change is confirmed by a repeat measurement, additional measurements must be taken at 2 and 3 hours postdose. If the observed change is sustained through the three post-dose measurements, it should be considered a clinically significant change, which must be reported as an adverse event.

Rescue Medication Usage: All medications used emergently by the subject to relieve constipation, will be captured during their participation in the study.

Bone Growth Assessments: BMD and BMC assessments will be performed during the study for those subjects enrolled in DXA Subgroup only.

Any subject demonstrating a decline in 4% in BMD at any skeletal site from Screening to End of Treatment should additionally undergo a follow-up DXA assessment 6 to 12 months later.

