8.5.3 Clinical Laboratory Tests

For clinical laboratory data, mean changes from pre-treatment to post-treatment visits will be summarized using descriptive statistics. Cross-tabulations analysis will be performed for laboratory parameters with reference normal ranges. The laboratory data will be categorized as low, within, and above the reference normal ranges. The summary tables will tabulate the number and percentage of subjects with pre-treatment values below/within/above the normal reference range versus minimum/maximum/final post-treatment values below/within/above the normal reference range. Normal reference ranges will also be provided in the summary display. Laboratory parameters that are not specified in the protocol will not be included in the analysis, but they will be provided in the individual subject listings.

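### The protocol's safety tables do not separate newly exposed children from lubiprostone continuers, and the reference visit for safety changes is not named

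*Combined protocol and SAP*

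**What the plan says.** Safety is the primary objective (protocol section 2.1). For adverse events, section 8.5.2 says "Adverse events will be summarized in terms of incidence per dose group and overall". Incidence there counts each child with at least one episode once, and a Fisher or chi-square p-value compares the two groups. The Synopsis, under Statistical Methodology, says "Adverse events will be summarized in terms of incidence by treatment group and overall" and uses the same grouping for laboratory data, examinations and vital signs.

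Two kinds of children enter. Under section 5.5.2, children randomised to lubiprostone in the preceding study keep the dose they held at rollover, while former-placebo children, identified through the IXRS, are assigned a dose by body weight. Section 4.1 requires every child to have completed the earlier 12-week treatment period. Section 4.2 excludes a child if "Subject has experienced an adverse event during the SAG/0211PFC-1131 study which the Investigator considers to be clinically significant" and the event would limit participation; the next two criteria do the same for changes in medical status and for laboratory abnormalities.

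On the reference visit, footnote 1 of the Schedule of Evaluations says "The End-of-Treatment Visit (V7) in study SAG/0211PFC-1131 will serve as the Enrolment Visit", and section 6.1.2 carries the Visit 7 vital signs, laboratory, examination and DXA results into Visit 9. Section 8.5.3 says "mean changes from pre-treatment to post-treatment visits will be summarized using descriptive statistics" without naming the visit. Sections 8.5.4 to 8.5.6 refer to baseline, also without naming a visit. Elsewhere an earlier reference is used: section 6.3 has a follow-up rule for a "decline in 4% in BMD at any skeletal site from Screening to End of Treatment", and section 8.6.2.7 takes the baseline for diary ratings from the preceding study's 2-week screening period.

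**The concern.** Continuers have completed 12 weeks on lubiprostone, and the entry criteria have removed those with a participation-limiting event on drug. For former-placebo children the same criteria say nothing about tolerance of lubiprostone. If some events cluster early in exposure, or if intolerant children do not roll over, the two groups have different risks in this study, and one pooled percentage describes neither.

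The dose comparison inherits the problem. Dose follows one rule in continuers and another in former-placebo children, so the proportion of new users need not be the same in the two dose groups. A difference between doses, or its absence, could then reflect prior exposure.

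For laboratory values, vital signs, examinations and bone measures, the result depends on a baseline that the protocol text leaves open. A Visit 7 baseline would hide, in continuers, any effect already present after 12 weeks on drug.

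**Working it through.** **The plan's own figure.** The only relevant number is the planned enrolment, "415 subjects who completed Study SAG/0211PFC-1131". Section 8.1 explains it by "The sample size goal is based on the expected attrition that would occur" but gives no attrition rate or target number retained, so 415 cannot be reproduced. Nothing here disputes it.

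**Inputs.** From the protocol: N = 415, 12 earlier weeks and 36 weeks in this study. Assumed, because the documents do not give them: the new-user share f, the event rates in new users and continuers (p_new, p_cont), and r, the fraction of a drug effect that still arises after Visit 7 in continuers.

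**Adverse events.** Pooled rate = f × p_new + (1 − f) × p_cont. For example, at f = 0.25 with 15% and 5%: 0.25 × 15% + 0.75 × 5% = 7.5%, which is 0.50 of 15%. Ratios to the new-user rate are in brackets.

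| f | New users of 415 | 15% vs 5% | 15% vs 10% | 15% vs 15% |
|---|---|---|---|---|
| 0.25 | 104 | 7.5% (0.50) | 11.3% (0.75) | 15% (1.00) |
| 1/3 | 138 | 8.3% (0.56) | 11.7% (0.78) | 15% (1.00) |
| 0.40 | 166 | 9.0% (0.60) | 12.0% (0.80) | 15% (1.00) |
| 0.50 | 208 | 10.0% (0.67) | 12.5% (0.83) | 15% (1.00) |

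**Dose comparison with no true dose effect.** Take 15% in new users and 5% in continuers at either dose. A dose group with 20% new users shows 0.20 × 15% + 0.80 × 5% = 7%. One with 50% shows 0.50 × 15% + 0.50 × 5% = 10%. The 3-point gap comes entirely from the mix.

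**Mean change, if Visit 7 is the reference.** Pooled change ÷ full effect = f + (1 − f) × r. For f from 0.25 to 0.50:

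- r = 0 (effect complete by Visit 7 in continuers): 0.25 to 0.50.
- r = 0.5: 0.625 to 0.75.
- r = 1: 1.00, no dilution.

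A reference before the first lubiprostone dose also removes this source of dilution.

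**Precision of a split table.** For a 15% rate in new users, the 95% half-width is 1.96 × √(0.15 × 0.85 / n): 6.9 points at n = 104 and 4.9 at n = 208. With no events observed, the 95% upper bound 1 − 0.05^(1/n) is 2.8% and 1.4% respectively, against 0.7% for all 415.

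**The case against.** The strongest reply is that the study is about long-term safety over 36 weeks. Incidence during the study in the enrolled population is a legitimate quantity, and new-user risk is not the declared target. That stands: a mixed population limits interpretation, and the pooled figure is not wrong for what it measures. But the tables as described cannot show whether the two groups differ, and the protocol adds between-dose tests that the mix can distort.

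Several stronger readings are tempting and are not supported:

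- A reader might infer that Visit 7 is the safety baseline. The protocol says only that Visit 7 assessments need not be repeated at Visit 9, which is a scheduling rule. The BMD rule uses Screening.
- A reader might conclude that prior treatment is never separated anywhere. Section 8 defers detail to a SAP whose text is not in the material supplied, so the finding covers the protocol text only. The specific deferrals (DXA subgroups, under-represented subgroups, missing data, centre effects) do not mention prior treatment or the safety baseline.
- A reader might state that safety results are biased downward. Neither shares nor rates are given, and with equal rates there is no dilution.
- A reader might call the former-placebo children the only clean first-exposure group. The preceding study was placebo-controlled, so its lubiprostone arm also provides first-exposure data, with a concurrent control. The former-placebo children here are selected too: they had to complete 12 weeks and meet the same exclusions.

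Some handling already exists: section 8.5.1 lists deaths, serious events and adverse terminations individually with timing, and section 8.4 summarises exposure. Listings do not replace incidence by prior exposure.

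**Conclusion.** The point holds in a limited form. The protocol text describes safety summaries by dose group and overall, with none by prior treatment, in a cohort that combines first-time users with selected continuers. Pooled incidence may understate the new-user risk, and the between-dose p-values may be confounded. Over the illustrated range the pooled rate is anywhere from half the new-user rate to equal to it; this is a sensitivity range, not a forecast, and its direction assumes that continuers' rates are no higher than new users'.

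Separately, the reference visit for safety changes is not named. If it is Visit 7, continuers are measured from an on-drug value, and how much of an effect is lost depends on how much had already appeared by Week 12. No figure in the protocol is wrong on this point. It is worth correcting because safety is the primary objective and the correction is cheap.

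**What to change.** In sections 8.5.2 to 8.5.6 and the SAP:

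1. Add summaries of adverse events, serious events, discontinuations, laboratory values, vital signs, examinations and DXA by prior treatment (placebo to lubiprostone; lubiprostone to lubiprostone), within dose group and overall. Use the IXRS assignment after unblinding, and state when prior assignment is released, since section 5.5.2 links only dose unblinding to database lock.
2. Add exposure-adjusted adverse event rates by time since first lubiprostone dose.
3. Stratify the between-dose tests by prior treatment, or drop the p-values.
4. Define the safety baseline as the last value before the first-ever lubiprostone dose in either study. Give change from Visit 7/9 as a second display. Show both separately by prior treatment.
5. Do not pool raw height, weight, BMD or BMC changes across prior-treatment groups. From a first-ever-dose baseline, continuers have about 12 + 36 = 48 weeks of change and former-placebo children 36, and these children are growing.

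The cost is SAP text, more tables and smaller denominators per column, with the loss of precision shown above. Sites and children are not affected.
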